[figure not shown]

## 1. List of terms

ABG – arterial blood gas  
AE — Adverse Event  
AHA — American Heart Association  
ASD – Antiseizure Drug  
BSAS — Bedside Shivering Assessment Scale  
CA — Cardiac Arrest  
CI – Co-investigator  
COSCA – Core Outcome Set for Cardiac Arrest  
CPC — Cerebral Performance Category  
CT — Computed Tomography  
ED – Emergency Department  
DNR — Do Not Resuscitate  
DSMC — Data Safety Monitoring Committee  
DWI – diffusion weighted imaging  
eCRF — electronic Case Report Form  
EEG — Electroencephalography  
EMSE – Epidemiology-based Mortality Score in Status Epilepticus  
EQ5D-5L — Euroqol health Survey 5 Dimensions 5 Level version  
ESICM – European Society of Intensive Care Medicine  
FOUR score — Full Outline of UnResponsiveness score  
GABA — Gamma-AminoButyric Acid  
GABA-t — Gamma-AminoButyric Acid transaminase  
GFAP — glial fibrillary acidic protein  
GOS — Glasgow Outcome Scale  
GOS-E — Glasgow Outcome Scale-Extended  
HRQOL – Health-related quality of life  
ICU — Intensive Care Unit  
IHCA — In-hospital cardiac arrest  
ILCOR — International Liaison Committee on Resuscitation  
IQCODE — Informant Questionnaire on Cognitive Decline in the Elderly  
MoCA — Montreal Cognitive Assessment  
mRS — modified Rankin Scale  
MRI — Magnetic Resonance Imaging  
NfL — Neurofilament Light chain  
NG/OG – nasogastric or orogastric  
NSE — Neuron Specific Enolase  
OHCA — Out-of-hospital Cardiac Arrest  
PASE — Post-Anoxic Status Epilepticus  
PI – Primary Investigator  
PD – Pharmacodynamics  
PK — Pharmacokinetics  
RASS — Richmond Agitation-Sedation Scale  
REMS — Risk Evaluation and Mitigation Strategy  
RN – Registered Nurse  
ROSC — Return of Spontaneous Circulation  
SAE — Serious Adverse Event  
SF-36 – 36-Item Short Form Survey  
SSEP — Somatosensory Evoked Potentials  
TTM — Targeted Temperature Management  
UCH-L1 — ubiquitin C-terminal hydrolase L1

## VIGAB-STAT IIa Protocol

UF – University of Florida

VFP – Visual Field Perimetry

VFQ-25 – Visual Function Questionnaire 25

VGB – Vigabatrin

WLST – Withdrawal of Life Supporting Therapies

WLST-N – Withdrawal of Life Supporting Therapies due to perceived poor neurologic prognosis

## 2. Trial overview

In 2015, the Institute of Medicine released a call to action for strategies to improve survival following cardiac arrest (**CA**)[1] given the lack of improvement in mortality rates and functional outcomes despite advances in resuscitation and the widespread use of targeted temperature management (**TTM**). By confirming the feasibility of using vigabatrin (**VGB**) as an early adjunct treatment for post-anoxic status epilepticus (**PASE**), while characterizing key pharmacokinetic and pharmacodynamics parameters in the post-CA setting, this trial pioneers the study of an innovative therapy for a deadly and frequent complication in the post-CA period.

The VIGAB-STAT study is a phase IIa trial exploring the feasibility of using VGB, a Gamma-AminoButyric Acid -transaminase (**GABAt**) inhibitor, as an early adjunct treatment for refractory seizures in CA survivors with PASE. This pilot trial aims to demonstrate the feasibility of enteral administration of a single load of VGB within targeted 48 hours of PASE onset in unconscious survivors of CA. The load of VGB is *in addition* to the load of a commonly used intravenous second-line therapy given at the discretion of the treating neurologist (e.g., phenytoin, valproic acid, phenobarbital, lacosamide, levetiracetam, etc). The key elements collected during phase IIa include: rates of screening, enrollment, and reasons for screen failure; ability to deliver VGB enterally within 48h of PASE onset; key pharmacokinetic parameters on absorption of VGB in this population and levels of other anti-seizure drugs; and ability to perform vision loss surveillance with taurine levels, Goldmann perimetry, and patient-oriented questionnaires.

## 3. Background and significance

### Natural history of post-anoxic status epilepticus

Cardiac arrest claims millions of lives annually across the globe. Outcomes depend on resuscitation efforts and on the severity of global brain injury resulting from cessation of circulation (primary insult) and ongoing injury due to mismatches between cerebral energy supply and demand (secondary brain injury). Once return of spontaneous circulation (**ROSC**) occurs, the treatment relies on mitigating cerebral energetic demand. TTM is one of such treatments, but there is not a widely accepted practice across all post-CA patient population. This is because recent evidence questioned its role in affecting neurologic outcomes at 6 months compared to targeted normothermia [2]. Seizures, synchronized electrical phenomena produced by cortical neurons, are common after CA and lead to a marked increase in the cerebral metabolic activity and potential secondary injury. In fact, one in three unconscious CA survivors that undergo TTM experience PASE; TTM has not been shown to alter the frequency of post-CA seizures. Recent evidence suggests that early and aggressive treatment of PASE may lead to not only improved survival, but also functional independence [3-6].

Historically, PASE has been associated with nearly 100% mortality[4, 7-9]; however, the CA literature is confounded by bias due to variability in the provision of aggressive care when a low chance for functional recovery is perceived. As a result, this population has been traditionally excluded from observational studies and clinical trials of status epilepticus[10-15], and the management of these subjects varies widely[16, 17]. Further, non-standardized PASE treatment has failed to improve outcomes[18], leaving the Institute of Medicine's call yet unfulfilled. Despite increasing awareness of the potential positive impact of aggressive treatment of PASE with reports of neurologically intact survival [3-6], therapeutic interventions remain largely unexplored.

Subjects who develop status epilepticus while in the hospital tend to be refractory to first-line therapy (i.e., benzodiazepines) and are less likely to survive and return to a functional state[19]. Outcomes are indirectly proportional to status epilepticus duration[20-22] and latency to treatment[23]. Besides significant morbidity and mortality, status epilepticus and its treatment are associated with high hospital costs and prolonged length-of-stay[24, 25]. Moreover, while less than 50% of all status epilepticus patients are treated with anesthetics[26-28], PASE subjects more often receive them for practical reasons—often as sedatives to tolerate mechanical ventilation. PASE is also more likely to require aggressive treatment to reach seizure control[29]. Midazolam and propofol infusions are the forefront of treatment for refractory status epilepticus[11, 30-32] and are also the most commonly used sedatives during TTM. Recent pre-clinical studies have demonstrated potential benefits of a combined therapeutic strategy in status epilepticus aiming for synergistic mechanisms of action[33, 34], which may reduce duration and exposure to anesthetics and mitigate their associated morbidity[27, 35]. By identifying a novel indication of a drug with high potential for synergism and virtually devoid of safety concerns during short-term therapy, this study is the stepping-stone to filling an important knowledge gap in the care of CA survivors.

#### Rationale for a therapeutic trial exploring the GABA-ergic pathway

The GABA pathway is key in seizure initiation and termination[36]. During status epilepticus, there is marked alteration of GABA metabolism in this region promoting excitatory pathways; the rate of GABA synthesis decreases[37], GABA turnover time increases up to 3-fold[37], and cell surface GABA receptors migrate to the intracellular space[38-40].

Emerging evidence suggests that early and aggressive treatment of PASE may lead to good outcomes in selected cases[3-6, 41]; however, no standardized treatment has been proven beneficial in this population[18], and therapeutic algorithms are largely extrapolated from convulsive status epilepticus guidelines. First-line therapy acts by enhancing the GABAA receptor to increase its inhibitory tone. Vigabatrin, 4-amino-5-hexenoic acid or gamma-vinyl GABA, is a structural analog of GABA and irreversibly inhibits GABA-t—the enzyme responsible for GABA catabolism, thereby increasing brain levels of GABA. Vigabatrin may also stimulate GABA release [42]. The overall net effect is a significant elevation in GABA levels in nerve terminals, which facilitates GABA-mediated synaptic transmissions and leads to a marked and sustained antiseizure effect [43]. Its efficacy as adjunct therapy for intractable epilepsy is well-established in the literature[44-50]. In addition to its direct anti-seizure effects, VGB may potentiate the therapeutic effects of GABAergic anesthetics and antiseizure drugs (**ASDs**)[51, 52] that are commonly used in the post-CA period (e.g., propofol, midazolam, and valproate). Currently, VGB is an FDA-approved therapy for infantile spasms and refractory focal-onset seizures in adults. It is also being investigated as a neuroprotective therapy in traumatic brain injury[53, 54], though its role as an adjunct therapy in status epilepticus is unclear.

**Rationale for chosen VGB regimen:** A single VGB load is sufficient to achieve a prolonged GABA catabolism inhibition[55] and minimizes the risk of vision loss associated with chronic exposure. No toxicity has been reported with a single dose of VGB to date. The inhibition of central and peripheral GABA-t has been shown to outlast serum VGB elimination[55-57], demonstrating the irreversible nature of GABA catabolism inhibition[57, 58]. Vigabatrin has been tested up to 6,000mg daily doses in studies [59], including a study comparing placebo, 1,000/day, 3,000/day, and 6,000/day for a total of 12 weeks [60]. Additionally, 6,000/d dosing led to a similar therapeutic effect on seizure control than 3,000/d [60], but it was associated with increase sedation/drowsiness and led to higher proportion of patients discontinuing therapy. A dose ceiling effect has been set in initial studies of VGB, in which doses >60mg/kg failed to elevate cerebral GABA levels further[61], and prolonged elevations of cerebral GABA levels may reduce

GABA synthesis [61]. In an individual ~70 kg, 60mg/kg corresponds to 4,200mg. As absorption is expected to be lower in the post-cardiac arrest period (due to decreased gastrointestinal motility and gastric emptying), a single dose of 4,500mg was selected for patients with normal or mild renal impairment. Patients with moderate (CrCl 30-50mL/min) will receive 2,250mg (50% dose reduction), and patients with severe renal impairment (CrCl<30cc/min) will receive 1,125mg (75% dose reduction). Thus, to minimize toxicity risk, maximize synergistic potential with co-administration of GABA-ergic anesthetics and the therapeutic window, we selected a single loading dose of VGB.

## 4. Trial hypotheses and outcomes

### Main objective and central hypothesis

Our overarching goal is to improve outcomes of successfully resuscitated individuals who experience refractory seizures following CA. Our central hypothesis is that early inhibition of GABA metabolism through VGB is possible in the post-CA period and may be an effective adjunct treatment for PASE.

### Specific aims and hypotheses

**Prove the feasibility of enteral administration of a VGB load within 48 hours of PASE onset in resuscitated CA subjects.** We hypothesize that administering a single load of VGB within 48 hours of PASE onset is feasible. Later study phases will assess the potential therapeutic effects of this intervention.

**Demonstrate the pharmacokinetics (PK) of VGB absorption in the post-CA period.** We will follow VGB levels serially in the post-CA setting, in which there may be delayed absorption and impaired clearance. Delayed absorption is anticipated due to continuous enteral feeding, prevalent delayed gastric emptying, enteric mobility, and decreased enteric blood flow in the setting of neuromuscular blockade and vasopressors. Impaired clearance may occur due to a high prevalence of renal insufficiency and older age. We hypothesize that VGB will be detectable in ≥80% and 100% of subjects by 3- and 12h, respectively. We expect that peak concentrations will be delayed from 1 to 3h post-VGB in older individuals (≥65-year-old) receiving continuous enteral feeding, and that delayed clearance (detectable VGB after 72h) will occur in CrCl ≤30cc/min[62-64].

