### Primary outcome

#### A. Primary feasibility outcome – enrollment and drug delivery

We will primarily be looking at the ability to deliver VGB in PASE subjects; the target will be administering 4,500mg (or dose adjusted in moderate and severe impairment) of VGB enterally within **48 hours of PASE onset** in ≥ 80% of enrolled subjects. Given the lack of well-established alternative treatments in this deadly disease, we anticipate 60-75% enrollment of eligible subjects, and will therefore be tracking the ratio between eligible and enrolled subjects, consent rates, and reasons for decline in study participation.

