#### C. Primary pharmacologic outcome: PK – absorption

By analyzing serial VGB levels including baseline, we will validate the drug assay and characterize drug absorption; the target will be achieving a detectable VGB level in the serum of ≥ 80% of

enrolled subjects by 3 hours post-load. We anticipate detectable levels in all subjects by 12 hours. We expect peak concentrations to be delayed by one to three hours in older individuals receiving continuous enteral tube feedings.

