## 6. Trial design

Phase IIa: This is a feasibility, single center, open-label pilot, with blinded outcome assessment, of early administration a single 4,500mg (or dose adjusted in moderate and severe impairment) VGB in 12 consecutive PASE subjects.

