## 12. Statistical plan and data analyses

### Phase IIa sample size

12 subjects from the University of Florida

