### Primary outcome

Descriptive statistics with rates and proportions will be obtained regarding feasibility outcomes. Regarding the PK outcome, we will use the noncompartmental method for pharmacokinetic analyses. The key pharmacokinetic parameters, maximum concentration in plasma ( $C_{max}$ ) and the time to reach

maximum concentration ( $T_{max}$ ) will be determined directly from the plasma concentration-time profile of each participant. The area under the VGB concentration-time curve in plasma from zero to the time of the last quantifiable concentration ( $AUC_{0-t_{lqc}}$ ) will be calculated using the linear trapezoidal methods, and the AUC will be extrapolated to infinity for the evaluation of  $AUC_{0-\infty}$ .

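### The aim is to prove feasibility against 80% targets, but 12 subjects can only estimate those rates, no interval is planned, and the delivery denominator is unsettled

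*Combined protocol and SAP*

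**What the plan says.** In section 4 (Specific aims and hypotheses) the first aim is to "Prove the feasibility of enteral administration of a VGB load within 48 hours of PASE onset". Primary outcome A sets the delivery target as dosing within 48 hours "in ≥ 80% of enrolled subjects". Primary outcome C sets the absorption target: "the target will be achieving a detectable VGB level in the serum of ≥ 80% of" enrolled subjects by 3 hours after the load. Primary outcome B adds two more targets: 90% completion of taurine levels, and reliable perimetry in at least 80% of survivors who regain consciousness.

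Section 12 gives the sample size as "12 subjects from the University of Florida", with no stated precision, confidence level or power. Power calculations are left out because the pilot does not aim to detect therapeutic effects. The analysis of the feasibility outcomes is one sentence: "Descriptive statistics with rates and proportions will be obtained regarding feasibility outcomes". No interval, confidence level, test or decision rule for these targets appears anywhere in the document.

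Section 6 describes giving "VGB in 12 consecutive PASE subjects". Its Drug administration text classes a subject as a screen failure if the drug is not given within 48 hours of onset.

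**The concern.** The verb in the aim promises more than a proportion from 12 subjects can deliver. A count that meets the target is compatible with true rates well below it, and the plan reports nothing that would show this. The reason given for omitting power concerns therapeutic effects. It does not cover the precision of the feasibility proportions, which are the primary outcomes.

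At stake is how the primary result is read. Without an interval, 10 of 12 may be taken as a demonstrated rate when it is a loose estimate. The delivery proportion has a further difficulty: if subjects who miss the 48-hour window leave the enrolled set, the proportion cannot fall below 100%, and an interval around it would mean nothing.

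**Working it through.** **Inputs.** N = 12 (sections 6 and 12). Targets: 80% for delivery, 3-hour detection and perimetry; 90% for taurine (section 4). The documents give no confidence level, so 95% is an assumption here. Because the plan gives no basis for N = 12, there is no stated calculation to reproduce.

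**Smallest counts that meet the targets.** 0.80 × 12 = 9.6, so 10/12 (83.3%) is needed; 9/12 is 75%. For taurine, if the unit is the subject, 0.90 × 12 = 10.8, so 11/12 (91.7%) is needed.

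**Exact limits.** For x successes in n, the two-sided 95% Clopper-Pearson limits are the 2.5% quantile of Beta(x, n − x + 1) and the 97.5% quantile of Beta(x + 1, n − x). When x = n, the lower limit reduces to 0.025^(1/n).

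| Result | Estimate | Exact 95% limits |
|---|---|---|
| 10/12 | 83.3% | 51.6% to 97.9% |
| 11/12 | 91.7% | 61.5% to 99.8% |
| 12/12 | 100% | 73.5% to 100% |

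At 12/12 the lower limit is 0.025^(1/12) = 0.735. The one-sided 95% bound is 0.05^(1/12) = 0.779. Equivalently, if the true rate is exactly 80%, 12/12 occurs with probability 0.8^12 = 0.069, so the best possible result does not reject 80% at the one-sided 5% level. All successes would first put the exact lower bound at or above 80% with n = 14 (one-sided, 0.8^14 = 0.044) or n = 17 (two-sided, 0.8^17 = 0.0225).

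**Dependence on method.** Lower 95% bounds at 12/12:
- below 80%: exact two-sided 73.5%, exact one-sided 77.9%, Wilson two-sided 75.8%, Agresti-Coull two-sided 71.8%
- above 80%: Jeffreys two-sided 81.5%, Wilson one-sided 81.6%, Jeffreys one-sided 85.5%

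At 10/12 every one of these bounds is far below 80%; the highest is 61.0% (Jeffreys one-sided).

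**How the 10/12 benchmark behaves.** P(X ≥ 10 | 12, p):

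| True rate | 50% | 60% | 65% | 70% | 80% | 90% | 95% |
|---|---|---|---|---|---|---|---|
| Benchmark met | 2% | 8% | 15% | 25% | 56% | 89% | 98% |

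**Perimetry.** The denominator is survivors who regain consciousness, and the documents give no number. Assuming 2 to 6, a perfect result has an exact lower limit from 0.025^(1/2) = 15.8% to 0.025^(1/6) = 54.1%.

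**Denominator for delivery.** The target counts enrolled subjects, while the screen-failure rule removes those not dosed in time. As an illustration only, suppose 15 subjects are enrolled by consent and 12 are dosed within 48 hours. Counting all enrolled gives 12/15 = 80% (exact 95% limits 51.9% to 95.7%). Dropping the three as screen failures gives 12/12 = 100%. The same data either just meet the target or meet it by construction. The 3-hour detection target also uses enrolled subjects, although a post-load level exists only in those dosed.

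**The case against.** The strongest reply is that this is a declared feasibility pilot with a descriptive analysis. 'Prove' attaches to feasibility in general, and the aim goes on to state a hypothesis. The 80% figures are called targets or goals. A lower bound under 80% is a defect only if the plan claims to exclude lower rates, and any reader can compute an interval from x/12.

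Much of this stands, and it rules out several stronger readings that a reader might infer:

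- *That the plan treats an observed 80% as proof of a true rate of 80% or more.* No passage says so.
- *That a go/no-go decision rests on these proportions.* The documents set no such rule. The uses they state for later phases are choosing clinical outcomes, informing eligibility criteria and exploring earlier dosing.
- *That N = 12 is an error.* Nothing in the plan commits to a precision that 12 fails to reach.
- *That the 56% chance of meeting the benchmark at a true 80% shows a small-sample weakness.* Any threshold placed at the true rate behaves in this way: the probability is 58% at n = 50, 56% at n = 100 and 53% at n = 500. The 10/12 benchmark also screens out clearly low rates, as the table shows.

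The reply does not remove the mismatch between the verb and the design, the missing interval, or the denominator conflict. If the targets are only benchmarks, the plan should say so.

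**Conclusion.** The concern holds as a matter of wording, reporting and denominator. Under exact two-sided 95% limits, no possible result in 12 subjects establishes a delivery or detection rate of at least 80%: the lower limit runs from 51.6% at the smallest qualifying count to 73.5% at a perfect score. This rests on an assumed 95% level, the exact method and a true denominator of 12. The statement about 12/12 changes under Jeffreys or one-sided Wilson limits, which is a reason to name the method beforehand; the statement about 10/12 does not change under any method checked. Perimetry will be less precise still. The consequence is moderate: no data collection or sample size needs to change, but what the primary outcomes can support does.

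**What to change.** 1. In the first aim, replace 'Prove' with 'Estimate' or 'Assess'.
2. Settle the denominators first. Reconcile the enrolled-subject denominator in primary outcome A with the screen-failure rule in Drug administration, so that enrolled subjects dosed late or not at all count as delivery failures. State whether 12 means enrolled or dosed, and whether 3-hour detection is counted among enrolled or dosed subjects. A fixed 10-of-12 criterion should not be written in until this is done.
3. In section 12, report every primary feasibility and detection proportion with its numerator, denominator and Clopper-Pearson 95% interval. Include perimetry among conscious survivors and the 90% taurine target. Define taurine completion per subject, because repeated samples within a subject are not independent.
4. State that the targets are point-estimate benchmarks, and that meeting one does not establish that the true rate reaches it.

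The cost is a few lines in the aims and the statistical section, with no change to sample, procedures or timeline. The downside is that the stated conclusion becomes less favourable, and delivery may fall below 100% once late or undosed subjects are counted.

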### Primary outcome

#### A. Primary feasibility outcome – enrollment and drug delivery

We will primarily be looking at the ability to deliver VGB in PASE subjects; the target will be administering 4,500mg (or dose adjusted in moderate and severe impairment) of VGB enterally within **48 hours of PASE onset** in ≥ 80% of enrolled subjects. Given the lack of well-established alternative treatments in this deadly disease, we anticipate 60-75% enrollment of eligible subjects, and will therefore be tracking the ratio between eligible and enrolled subjects, consent rates, and reasons for decline in study participation.

